**Outcome Measures**

1. Self-described discomfort level using 4-point verbal pain scale (None, mild, moderate, severe)

2. Observer-graded discomfort level (Nonverbal vocal complaints, verbal vocal complaints, facial grimace/winces, and restlessness/withdrawal)
3. Post-procedure recall of discomfort using 4-point verbal pain scale (same as #1)

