### **Objectives**

We expect that tourniquet lidocaine will be superior to straight non-tourniquet lidocaine in reducing propofol injection pain. We also want to determine the association of tourniquet duration on reduction of pain with propofol administration. Small studies indicate that 60 seconds of tourniquet lidocaine is superior to 30 seconds or less of tourniquet duration or mixed lidocaine/propofol for injection. We suspect many clinicians do not use the 60-second tourniquet technique due to the extra time involved but hypothesize that a more practical application by applying the tourniquet as soon as the patient is positioned on the operating table will not only be more widely adopted by clinicians as it does not cause delay but also provide the necessary amount of time for benefit from the tourniquet. We plan to record the time from tourniquet application to start of propofol administration, which we predict will be at least 60 seconds, and see if there is a correlation between duration of venous stasis of IV lidocaine and pain benefit.

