### **Subjects selection criteria • Inclusion Criteria**

Any patient aged  $\geq 18$  years scheduled to receive propofol as part of their sedation or anesthetic.

- **Exclusion Criteria**

Since children (age < 18 years) frequently receive induction of anesthesia by mask, they will be excluded.

Any patient receiving pre-medications prior to their sedation that could alter their recall or perception of the pain such as fentanyl or midazolam.

- **Sample Size**

We estimate that 25 subjects in each of the two groups will be required to test the hypothesis based on prior studies.

**Interventions and Interactions** •

There will be two groups: ○ Group 1: 50mg of 2% lidocaine given just prior to the propofol dose through the IV line.

○ Group 2: 50mg of 2% lidocaine given IV with venous occlusion applied when the patient is positioned on the operating room table and timed until the onset of propofol administration. The tourniquet will either be a latex free tourniquet or McKesson Quick Release tourniquet applied to the forearm 10cm distal to the elbow joint in the tourniquet group. Venous stasis will be confirmed with cessation of flow from hanging IV fluid.

- For both groups, no premedication shall be given, which is the normal practice for these procedures. Study procedures will involve a 20 gauge intravenous (IV) catheter placed in a vein distal to the mid forearm. Venous occlusion will be achieved by either a latex free tourniquet or McKesson Quick Release tourniquet applied to the forearm 10cm distal to the elbow joint. Tourniquet pressure will be somewhat variable but sufficient to cause venous stasis as confirmed by no flow of hanging IV fluid. Injections will be delivered at roughly 1 ml/sec.
- For studies involving interactions the survey, questionnaire or method of observation should be described.
  - Please see Data Collection Form Attached

- The time required should occur within their usual anesthetic parameters and should not delay their procedure nor increase the duration of anesthesia significantly.

- Table illustrating the schedule of events in the study:

Day prior to the procedure	Describe study to the patient by telephone
Day of procedure: holding area	Consent patient for
Day of procedure: holding area	Randomly assign patient to one of two groups

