Day of procedure: procedure area	Accompany patient to the operating or procedure room, perform instructions from the group they are assigned to while noting outcome measures such as self-described discomfort and observer graded discomfort
Day of procedure: recovery area	Revisit patient in recovery to determine post-procedure recall of discomfort
Post-study period	Analyze data

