### **Analytical Plan**

We will analyze results initially using descriptive statistics. Comparison between groups will be done using chi square tests for proportions, and t-tests or ANOVA procedures for continuous variables. Regression analysis will be performed to identify independent outcome predictors. Other inferential statistical analysis will be conducted as appropriate.

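### One superiority hypothesis, three discomfort outcomes, and no primary outcome, significance level or multiplicity rule to say which one decides

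*Combined protocol and SAP*

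**What the plan says.** The Objectives give one directional claim: "We expect that tourniquet lidocaine will be superior to straight non-tourniquet lidocaine in reducing propofol injection pain". They do not say which measure of pain decides it.

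Outcome Measures then numbers three outcomes and calls none of them primary or secondary:

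- The first is the patient's own rating while the drug goes in: "Self-described discomfort level using 4-point verbal pain scale (None, mild, moderate, severe".
- The second is a rating made by someone watching the patient: "Observer-graded discomfort level (Nonverbal vocal complaints, verbal vocal complaints, facial grimace/winces, and restlessness/withdrawal".
- The third is what the patient remembers afterwards: "Post-procedure recall of discomfort using 4-point verbal pain scale (same as #1".

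The schedule of events names the first two together: "noting outcome measures such as self-described discomfort and observer graded discomfort". The data collection form in the Appendix records all three and ranks none.

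The Analytical Plan describes tests by type of variable: "Comparison between groups will be done using chi square tests for proportions, and t-tests or ANOVA procedures for continuous variables". It links no test to an outcome, states no significance level or sidedness, and leaves the list open: "Other inferential statistical analysis will be conducted as appropriate".

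The sample size statement refers back to a single hypothesis without naming the outcome behind it: "We estimate that 25 subjects in each of the two groups will be required to test the hypothesis based on prior studies".

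**The concern.** A single hypothesis needs a single decision rule, and this plan has none. It does not say that one significant outcome out of three is enough, but it does not exclude that reading either. If the deciding outcome is chosen after the results are known, the error rate of the superiority claim is no longer controlled, and no later adjustment can restore it.

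The second problem is discordance. Self-report at injection, observed behaviour and recall before discharge are different measurements, and with 25 patients per group they can easily disagree. If recall favours the tourniquet and self-report does not, the plan offers no way to say whether the hypothesis was supported.

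**Working it through.** **The plan's own figure.** The 25 per group cannot be reproduced, because no significance level, power, effect size, event rate, standard deviation or deciding outcome is given. For illustration only, at two-sided 0.05 and 80% power, 25 per group corresponds to a standardised difference of 0.80. Comparing proportions, 60% against 20% needs 23 per group and 50% against 15% needs 27. The sample size therefore does not reveal an implied primary outcome.

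**Inputs.**

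- From Outcome Measures: three outcomes, counted as one test each.
- Assumed: each test two-sided at 0.05, so 0.025 in the direction favouring the tourniquet.
- Assumed: a common correlation ρ between the three test statistics, from 0 to 0.9.
- Assumed: any one significant outcome may support the claim.

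**Independent tests (ρ = 0).**

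- Favouring the tourniquet: 1 − 0.975³ = 1 − 0.9269 = 0.0731.
- Either direction: 1 − 0.95³ = 1 − 0.8574 = 0.1426.

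**Correlated tests.** With equicorrelated normal test statistics, the chance of at least one false result favouring the tourniquet is

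1 − ∫ φ(x) · Φ((1.96 − √ρ·x)/√(1 − ρ))³ dx.

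The either-direction version replaces the Φ term by the probability of lying between −1.96 and 1.96, given x.

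| ρ between test statistics | Favouring tourniquet | Either direction |
|---|---|---|
| 0 | 7.3% | 14.3% |
| 0.3 | 6.8% | 13.6% |
| 0.5 | 6.3% | 12.5% |
| 0.7 | 5.5% | 10.9% |
| 0.9 | 4.2% | 8.4% |
| One primary outcome | 2.5% | 5.0% |

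The directional inflation is a factor of 4.18/2.5 = 1.7 at ρ = 0.9 and 7.31/2.5 = 2.9 at ρ = 0.

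**How often would outcomes 2 or 3 overrule outcome 1 by chance?** This was simulated with 40,000 trials per setting, no true effect, 25 per arm and the Wilcoxon rank-sum test (normal approximation, corrected for ties). Assumed inputs were shares of 45/30/15/10% across the four pain levels and 25% prevalence for each observed sign. The observer outcome was scored as the number of signs, for the simulation only. Correlation here is that of the underlying latent variables. It is not the ρ above: at latent 0.9 the test statistics correlate at about 0.79.

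| Latent correlation | At least one of three favours tourniquet | Observer score or recall favours tourniquet, self-report not significant | The same, either direction |
|---|---|---|---|
| 0 | 7.4% | 4.7% | 9.2% |
| 0.3 | 6.9% | 4.4% | 8.8% |
| 0.5 | 6.2% | 3.7% | 7.7% |
| 0.7 | 5.8% | 3.3% | 6.5% |
| 0.9 | 4.9% | 2.4% | 4.8% |

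Self-report tested alone gave 2.4–2.6% favouring the tourniquet and 4.9–5.0% in either direction. Naming one primary outcome therefore brings the error back to its nominal size.

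**Sensitivity to scoring.** With the observer outcome scored as any sign against none, the third column becomes 4.9%, 5.0%, 4.4%, 4.0% and 2.8%. The figures move a little; the conclusion does not.

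**The case against.** The strongest reply is that the percentages describe a rule the plan does not contain. They need a significance level, a correlation and permission for any one outcome to decide, and none of these is written down. That is true, and the figures should be read as conditional. The missing rule is nevertheless the defect itself, and the calculation shows what its absence permits.

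Self-described discomfort is listed first in the schedule, in Outcome Measures and on the form, and is the most direct measure of injection pain, so it could be taken as the implicit primary. Position in a list is not designation. If it is what the investigators intend, one sentence settles it.

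The upper end of the range is also unlikely. Recall uses the same scale for the same event, and the observer form counts a spoken complaint of pain, so positive correlation is to be expected. At ρ from 0.7 to 0.9 the excess over 2.5% is 3.0 to 1.7 percentage points, not 4.8. That stands. The either-direction figures also matter less, because the hypothesis is directional.

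Finally, the simulation uses a Wilcoxon test, which the plan does not name. A repeat under the same assumed shares, with chi-square tests of any against no discomfort, gave 6.6–8.7% without continuity correction (single test about 3.0–3.3%) and 3.3–4.5% with it (single test about 1.5–1.6%). So 4.2–7.3% does not bound the plan's actual error rate. A roughly two- to threefold inflation appears in both versions. Counting one test per outcome may also understate the exposure: the observer outcome has four behaviours and no scoring rule, and the four-level scales can be cut in several ways.

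**Conclusion.** The concern holds. The documents state one superiority hypothesis and three outcomes that could decide it, with no primary outcome, significance level or multiplicity rule anywhere. If any one outcome may decide, a false finding in favour of the tourniquet has a 4.2% to 7.3% chance instead of 2.5%, for test-statistic correlation from 0.9 down to 0 and an assumed two-sided 0.05 per test. The exact figure depends on those assumptions and on the test used; the direction does not. Separately, discordant results would have no predefined interpretation, whatever the correlation.

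**What to change.** In Outcome Measures, name one outcome as the sole primary outcome that decides the superiority hypothesis; outcome 1, self-described discomfort during injection, is the natural candidate. In the Analytical Plan, state that it is tested two-sided at 0.05 with one pre-specified test suited to a four-level ordered scale, such as the Wilcoxon rank-sum test. Label the observer grading, recall and all other inferential analyses as secondary or exploratory, and say that they cannot establish superiority on their own.

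A fixed testing order or an adjusted level across the three outcomes would also control the error; a single primary is the simplest for 25 per group. The choice of test is a lesser matter than the choice of outcome. In a check at 25 per arm, with an assumed odds ratio of 3 and level shares of 45/30/15/10%, Wilcoxon had about 49% power against 31% for a four-category chi-square, but gained little over a t-test or a dichotomised chi-square. Fixing one test matters because it removes a further choice after the data are seen.

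The cost is a few sentences in two sections, with no new patients, data or procedures, provided it is done before outcome data are examined. The downside is that a significant result on the observer outcome or on recall alone would no longer support a superiority claim.

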### **Analytical Plan**

We will analyze results initially using descriptive statistics. Comparison between groups will be done using chi square tests for proportions, and t-tests or ANOVA procedures for continuous variables. Regression analysis will be performed to identify independent outcome predictors. Other inferential statistical analysis will be conducted as appropriate.

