**Appendix**

**Intravenous Lidocaine to Reduce Propofol Injection Pain:  
A Comparison of Two Methods**

MRN: \_\_\_\_\_

Date: \_\_\_\_\_

Observer: \_\_\_\_\_

PMH:	Chronic Pain Syndrome:	Y/N
	Daily use of Opioids:	
Y/ N		

Group (check one):             A (no tourniquet)             B (tourniquet)

Self-described discomfort level during injection using 4-point verbal pain scale:

- None
- Mild
- Moderate
- Severe

Investigator Assessments:

1) Induction Discomfort Scale (during injection and within 5 seconds after injection)

Grimace

IV forearm withdrawal

Moaning

Verbal statement of discomfort (“it hurts”, etc.)

2) Post-Procedure Discomfort Scale (in Recovery Area just prior to discharge).

I recall \_\_\_\_\_ discomfort in my IV arm while I went to sleep:

No

Mild

Moderate

Severe

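### No test, cut-point or scoring is fixed for the two ordered 4-point pain outcomes, and the chi-square tests the plan offers can lose substantial power against a rank test

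*Combined protocol and SAP*

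**What the plan says.** The Objectives section states a superiority aim: "We expect that tourniquet lidocaine will be superior to straight non-tourniquet lidocaine in reducing propofol injection pain". Outcome Measures lists two patient-reported outcomes on the same four ordered words:

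- Outcome 1: "Self-described discomfort level using 4-point verbal pain scale (None, mild, moderate, severe".
- Outcome 3: "Post-procedure recall of discomfort using 4-point verbal pain scale (same as #1".

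The data form in the Appendix collects them under "Self-described discomfort level during injection using 4-point verbal pain scale" and "Post-Procedure Discomfort Scale (in Recovery Area just prior to discharge". Both are tick-lists of four words, with no numeric scores and no threshold.

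The Analytical Plan gives the between-group tests in one sentence: "Comparison between groups will be done using chi square tests for proportions, and t-tests or ANOVA procedures for continuous variables". It then promises a regression of unstated type and closes with "Other inferential statistical analysis will be conducted as appropriate". No sentence links a test to an outcome.

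On size, the Sample Size item says: "We estimate that 25 subjects in each of the two groups will be required to test the hypothesis based on prior studies". It gives no rate, effect, significance level or power.

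**The concern.** A four-category ordered scale is neither a single proportion nor a continuous variable, so the stated rule does not determine its analysis. At least three chi-square analyses fit the wording: the full 2x4 table, any pain versus none, and moderate or severe versus less. A t-test would need a 0-3 scoring that appears nowhere, so it is a less natural fourth reading.

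Two things are at stake. First, the 2x4 chi-square gives the same p-value however the four columns are arranged. It therefore spends three degrees of freedom on a question about direction. Second, with 50 patients, whether the superiority claim is supported can depend on a choice that the plan leaves open.

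**Working it through.** **Can the sample size reveal the intended test?** No. With two-sided 5% and 80% power (both assumed) and no continuity correction, 60% versus 21% needs 24 per group, and so does 50% versus 13%. A standardised mean difference of 0.80 needs 2(1.96 + 0.84)²/0.80² = 24.5, so 25. The planned 25 fits binary and continuous contrasts alike, and can be neither reproduced nor refuted.

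**One invented table (none/mild/moderate/severe): 5/7/8/5 without tourniquet, 12/7/4/2 with.** Column totals are 17, 14, 12 and 7, and expected counts are half of these.

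- 2x4 chi-square: 2 × (3.5²/8.5 + 0²/7 + 2²/6 + 1.5²/3.5) = 5.50 on 3 df, p = 0.139. Shuffling the categories leaves this unchanged.
- Any pain, 20/25 versus 13/25: 50 × (5×13 − 20×12)²/(17×33×25×25) = 4.37, p = 0.037.
- Moderate or severe, 13/25 versus 6/25: 50 × (12×6 − 13×19)²/(31×19×25×25) = 4.16, p = 0.041.
- Wilcoxon: the midranks are 9, 24.5, 37.5 and 47. The rank sum is 5×9 + 7×24.5 + 8×37.5 + 5×47 = 751.5, and its null mean is 25×51/2 = 637.5. The tie-corrected variance is (625/12)(51 − 9678/2450) = 2450.5, so z = 114/49.5 = 2.30 and p = 0.021.

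**Power by simulation.** Only the 25 per group comes from the plan. The rest is assumed: two-sided 5%, proportional odds (each cumulative odds in the tourniquet group is OR times that in controls), 20,000 to 40,000 trials per scenario, and 2x2 tests without continuity correction. For example, control 40/30/20/10 with OR 4 gives about 73/18/7/3. The last column is the share of trials in which the three chi-square readings do not all agree on significance.

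| Control % | OR | Wilcoxon | 2x4 | Any pain | Mod/severe | Disagree |
|---|---|---|---|---|---|---|
| 50/25/15/10 | 4 | 63.3 | 42.5 | 63.9 | 40.4 | 43.3 |
| 50/25/15/10 | 5 | 74.1 | 53.3 | 74.2 | 48.3 | 43.5 |
| 40/30/20/10 | 4 | 69.6 | 49.4 | 70.3 | 46.7 | 43.8 |
| 40/30/20/10 | 5 | 80.2 | 61.7 | 80.5 | 55.8 | 41.0 |
| 30/30/25/15 | 4 | 73.0 | 54.7 | 71.0 | 56.1 | 38.6 |
| 30/30/25/15 | 5 | 83.6 | 67.6 | 82.3 | 66.3 | 34.2 |
| 15/30/35/20 | 4 | 75.2 | 57.0 | 56.9 | 67.6 | 39.2 |
| 15/30/35/20 | 5 | 86.2 | 70.4 | 71.7 | 77.5 | 31.8 |
| 10/25/40/25 | 4 | 75.0 | 56.7 | 47.0 | 71.2 | 44.0 |
| 10/25/40/25 | 5 | 86.0 | 71.0 | 62.0 | 82.0 | 36.9 |

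Entries move by up to about one point with a different seed. Losses against Wilcoxon:

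- 2x4: from 86.0 − 71.0 = 15 to 74.1 − 53.3 = 21 points.
- Any pain: within about 2 points when 30 to 50% of controls report none, but from 86.2 − 71.7 = 14 to 75.0 − 47.0 = 28 points when 10 to 15% do.
- Moderate or severe: from 75.0 − 71.2 = 4 to 74.1 − 48.3 = 26 points.

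At smaller effects (first three distributions) the 2x4 loss is about 18 points at OR 3 and 10 points at OR 2.

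**No true effect (first three distributions).** Wilcoxon rejects in 4.8 to 5.0% of trials, the 2x4 test in 4.3 to 4.8%, any pain in 5.5 to 6.7% and moderate/severe in 5.5 to 5.9%. Part of the apparent parity of any pain in the first six rows therefore comes from a mildly liberal test.

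**The case against.** The strongest reply is that chi-square is a legitimate choice, that the regression and catch-all sentences leave room for an ordinal method, and that every power figure rests on assumed distributions under proportional odds, where a rank test is near its best. Much of this stands. Wilcoxon does not always win. For 40/30/20/10 versus 80/5/5/10, where the effect is not a consistent shift, power is about 70% for Wilcoxon, 80% for the 2x4 test and 87% for any pain. But permitting a method is not the same as fixing one, and the gap in the text needs no simulation to be seen.

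A reader might infer more than the documents support:

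- *That the plan commits to a 2x4 chi-square.* It does not. That is one reading among several.
- *That failing to name an ordinal test is itself an error.* A cut-point fixed in advance can do as well as Wilcoxon under some control distributions. The trouble is that nothing in the documents says which distribution to expect.
- *That the 2x4 test is invalid because of small expected counts.* Small counts are common at this size, but how common depends on the distribution (59% of trials for a flat distribution with no effect, over 99% in others). The null rate of 4.3 to 4.8% shows no inflation.
- *That the false-positive rate is about 12%.* That is what picking the best of the three chi-square readings after seeing the data would give (11.7 to 12.2%). The plan does not say this will be done.
- *That the t-test, ANOVA and regression wording is misplaced.* The Objectives call for recording tourniquet time and relating it to pain, so that wording has a use.

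**Conclusion.** The concern holds for outcomes 1 and 3. It does not extend to the observer-graded outcome. That no test, cut-point or scoring is fixed can be read directly from the text. The size is conditional on the assumptions above. For odds ratios of 4 to 5, the 2x4 chi-square costs about 15 to 21 points of power against Wilcoxon in all five control distributions. The cost of a cut-point ranges from nothing to about 28 points, depending on where it is placed and on a control distribution that the documents do not give. The three chi-square readings disagree on significance in about 32 to 44% of trials.

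The plan should be changed, because a better-suited test is available at almost no cost. The gap weakens interpretation and possibly power, but does not invalidate the trial. Confidence is high on the omission and lower on the exact magnitudes.

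**What to change.** In the Analytical Plan, before data are seen, add:

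> Outcomes 1 and 3 will each be compared between groups with the tie-corrected Wilcoxon-Mann-Whitney test (two-sided 5%), whose p-value is used for inference. A proportional-odds common odds ratio with 95% CI will be given as a descriptive summary. Outcome 1 is the main comparison and outcome 3 is supportive.

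Keep the chi-square wording for binary items, and the t-test, ANOVA and regression wording for continuous variables and tourniquet time.

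The last added sentence is needed because fixing the test does not settle which outcome carries the claim. If both were tested at 5% and either counted, the null rate would be about 8 to 10% (control 40/30/20/10, latent correlation 0.9 down to 0). Outcome 1 is proposed because it is listed first and refers to the injection itself. The text also says which p-value decides, because the odds-ratio interval and the Wilcoxon test can disagree (0.1 to 1.4% of simulated trials).

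The cost is wording only, with no added patients, data or procedures. There are two downsides. An odds ratio is less familiar to readers than a difference in proportions, and a rank test gives up power when the effect is not a consistent shift along the scale.

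### The only regression is a search for predictors in about 50 patients, and the tourniquet comparison is never adjusted for the two baseline factors the form already records

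*Combined protocol and SAP*

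**What the plan says.** The Analytical Plan starts with descriptive statistics and then sets out the group tests: "Comparison between groups will be done using chi square tests for proportions, and t-tests or ANOVA procedures for continuous variables". None of these is adjusted for a baseline factor. Its one regression has a single stated purpose: "Regression analysis will be performed to identify independent outcome predictors". The outcome, the type of model, the candidate variables, the selection rule and the role of treatment group are all left open. The section closes with "Other inferential statistical analysis will be conducted as appropriate".

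On sample size, the protocol says "We estimate that 25 subjects in each of the two groups will be required to test the hypothesis based on prior studies", which makes 50 in total. The data collection form in the Appendix records "Chronic Pain Syndrome" and "Daily use of Opioids" as yes/no items, and the Analytical Plan mentions neither. The main hypothesis in the Objectives is a treatment contrast, namely that lidocaine with a tourniquet is superior to lidocaine without one. A further aim reads "We also want to determine the association of tourniquet duration on reduction of pain with propofol administration". It is described there as a correlation and is not tied to the regression.

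**The concern.** The trial's question is how much the tourniquet reduces injection pain. The regression is pointed elsewhere, at finding which variables predict pain. A search of that kind in 50 patients errs in both directions: variables with no effect are declared predictors, and real ones are missed. With group not guaranteed a place in the model, the result also says little about the treatment.

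Meanwhile, two factors that may plausibly affect reported pain are collected at baseline and put to no stated use. Adjusting the treatment comparison for them needs no new data. If they are prognostic, leaving them out makes the comparison less precise in a trial with little precision to spare.

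**Working it through.** **Inputs from the documents.** 25 per group, 50 in total; a 4-level ordered self-described pain score; two yes/no baseline factors. The plan states no pain rates, effect size, SD, alpha, power or factor prevalence, so its 25 per group cannot be reproduced. That is a separate matter and is not needed here. Every rate and effect below is an assumption, with alpha taken as two-sided 0.05.

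**1. False predictors.** With k independent candidates that have no effect, the chance of at least one false finding is 1 − 0.95^k.
- k = 3: 1 − 0.857 = 14%
- k = 5: 1 − 0.774 = 23%

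Simulated backward elimination at p < 0.05 with n = 50 and pure-noise candidates (3,000 runs each) kept at least one in 14% and 23% of runs.

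**2. Missed predictors.** If pain is dichotomised and 20% to 50% of patients have it, there are 10 to 25 events. Three terms then have 10/3 = 3.3 to 25/3 = 8.3 events each; five terms have 2 to 5. Power to detect a real yes/no predictor (pain 60% with it, 30% without) is 28%, 42% and 51% when 10%, 20% and 30% of patients have it.

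**3. What adjustment would gain.** Continuous pain scores were simulated with 25 per group, a treatment effect of 0.8 residual SD, and the same shift in pain for each factor. For scale, the difference detectable with 80% power is (1.960 + 0.842) × √(2/25) = 0.79 SD. Opioid use was made to correlate with chronic pain, at 0.8 times its prevalence. Each cell gives power unadjusted → adjusted, from 3,000 runs.

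| Shift per factor | Chronic pain 10% | 20% | 30% |
|---|---|---|---|
| 0 | 79.0% → 77.6% | 80.0% → 77.6% | 79.3% → 77.4% |
| 0.5 SD | 76.3% → 77.3% | 74.8% → 77.7% | 72.1% → 77.5% |
| 1 SD | 70.0% → 77.7% | 61.4% → 77.3% | 57.3% → 76.4% |

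The change runs from a loss of about 1 to 2 points to a gain of about 19. In the most favourable cell the mean standard error of the group effect falls from 0.361 to 0.287. With no prognostic effect at 10% prevalence it rises from 0.280 to 0.286. The Monte Carlo error of one power figure near 80% is √(0.8 × 0.2/3000) = 0.7 points.

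**4. The ordinal model itself.** The table uses a linear model, so the proposed model was also simulated, with an assumed group log odds ratio of −1.5 and factor prevalence of 10% to 20%. Power was about 67% to 78%, against 43% to 56% for a chi-square test on the four levels. Compared with an unadjusted ordinal model, adjustment changed power by −1 to +8 points. Most of the advantage over chi-square therefore comes from using the order of the scale, and a smaller part from the covariates.

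**5. Sparse factors.** If 10% of patients have a factor, the binomial chance that fewer than 5 of 50 have it is 43%. For two independent factors, the chance that at least one is that sparse is 1 − (1 − 0.431)² = 68%. At 5% prevalence the single-factor chance is 90% and the two-factor chance is 1 − (1 − 0.896)² = 99%. A merged factor (either present) then has prevalence 1 − 0.95² = 9.75% and still falls below 5 patients in about 45% of trials. A fallback rule is therefore essential.

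**The case against.** The strongest reply is that the plan already answers its question. The groups are compared directly, that comparison is valid under randomisation, and the regression is an addition to it. This stands: it would be wrong to infer that the predictor search replaces the treatment comparison, or that an odd regression coefficient would cancel a difference shown by the group test.

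It can also be said that the open wording does not exclude a model with group and both factors. That is true, but nothing requires group to stay in or makes its effect the target. The 5% threshold behind the false-predictor figures is assumed, and the largest gain needs each factor to shift pain by a full SD. Both limits stand.

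A reader might go further and infer that tourniquet duration will enter the regression beside group and wreck the group estimate. Duration exists only in Group 2. Coded as 0 in Group 1, it correlates with group at 0.92 to 0.98 under the assumed duration distributions, and the standard error of the group effect rises 2.6 to 5.2 times. The documents do not support this as a finding. No section puts group and duration in one model, and the Objectives treat duration as a separate correlation. The inflation also depends on that coding, under which the group coefficient becomes an effect extrapolated to zero seconds. With duration centred within Group 2, the standard error ratio is 1.00. This is a reason for a precaution only.

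**Conclusion.** The concern holds as a matter of precision and interpretability. The plan's only regression is an unspecified predictor search, and the treatment comparison takes no account of two factors already on the form. On the assumptions above, the search has a 14% to 23% chance of a false predictor with 3 to 5 noise candidates. A fixed adjusted model costs about 1 to 2 points of power at worst and gains up to about 19 in the linear simulation; in the ordinal simulation the change from adjustment is −1 to +8 points. The real gain depends on prevalence and prognostic strength that the documents do not give, and it could be nil. The planned group tests remain unbiased. The change is worth making because it is nearly free and turns an open search into an estimate of the effect the trial was set up to measure.

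**What to change.** Replace the regression sentence in the Analytical Plan with a specification along these lines:

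- **Model.** Proportional-odds regression of the self-described 4-point score during injection on group, chronic pain syndrome (Y/N) and daily opioid use (Y/N). Group is always retained and there is no variable selection. Report the group odds ratio with a 95% CI.
- **Sparse factors.** If either factor is present in fewer than 5 patients, counted over both groups, use one merged covariate (either factor, Y/N). If that is also present in fewer than 5, fit group alone. The rule uses covariate counts only and can be applied before outcomes are seen.
- **Hierarchy.** This model is the main treatment comparison for that outcome; the chi-square and t-tests are supportive. Covariate coefficients are descriptive only.
- **Duration.** Analyse tourniquet duration only within Group 2.

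The cost is one replaced sentence and no new data. The open-ended predictor search is given up, and about 1 to 2 points of power may be lost if the factors are not prognostic. The odds ratio is conditional on the covariates and rests on proportional odds, which 50 patients can check only weakly; the report should say so.
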